15.1.2 Primary and Secondary Outcomes (Endpoints)

The primary (feasibility) outcome measure is the percentage of participants who obtain at least 20 rTMS treatment sessions over the 8-week treatment period. The primary outcome measure does not consider whether a participant was randomized with CUD or MUD.

The secondary (efficacy) outcome measure for each participant is the number and percent of weekly negative UDS results over the treatment period. The last UDS collected in a study week is used for that week. A UDS will be considered as negative for participants with primary CUD if it indicates no cocaine use. A UDS will be considered as negative for participants with primary MUD if it indicates no methamphetamine use.

Exploratory outcomes may include, and are not limited to:

- Other feasibility measures:
 - Percent of participants that complete at least 75% of daily monitoring
 - Percent of participants that complete all follow-up visits
- Self-reported cocaine and methamphetamine use (Timeline Follow-Back)
- Cocaine and/or methamphetamine craving (VAS)
- Depression/anxiety symptoms (Hospital Anxiety and Depression Scale)
- Sleep quality (Actigraphy, Pittsburgh Sleep Quality Index)
- Quality of life (HRQOL-4 quality of life assessment)
- Impact of personal characteristics (age, handedness) on treatment outcomes
- CBT participation
- Motor threshold changes over the treatment course

15.1.3 Recruitment

A total of approximately 160 individuals with moderate to severe cocaine (approximately N=80) and methamphetamine (approximately N=80) use disorder who have an interest in cutting down or stopping their use will be recruited (up to 80 participants per site; no more than 160 participants total). This sample size provides adequately sized 95% confidence intervals for the primary outcome and greater than 80% power to detect medium-sized effect sizes, measured as odds ratios, of greater than 4 with a two-sided hypothesis test and significance level of 0.05 for the secondary (efficacy) outcome for both CUD and MUD.

15.1.4 Randomization and Factors for Stratification

Randomization will be stratified based on study site, MDE, and whether the participant enters on primary CUD or MUD. The sample size within each of CUD and MUD is assumed to be 80. Following determination of full study eligibility via screening, and completion of baseline assessments, participants will be randomly assigned to one of the two conditions (rTMS or sham) for 8 weeks of treatment. Random assignment will be on a 1:1 ratio to one of the two conditions. Randomization will be stratified by study site, MDE, and CUD or MUD primary group designation. The randomization procedure will be conducted centrally through the CTN DSC, and randomization assignments will not be conveyed to research staff (including rTMS Operators) or participants. The DSC statistician will generate the randomization schedule using balanced blocks of varying sizes within strata to ensure lack of predictability along with relative equality of assignments across treatment groups. The DSC statistician will review randomization data on a regular basis to ensure that the scheme is being implemented according to plan. A randomization slot, once used, will not be re-allocated due to the intent-to-treat nature of the study.

15.2 Rationale For Sample Size and Statistical Power

The rationale for the sample size is broken into two parts: precision analysis for the primary (feasibility) outcome and typical power analysis for the secondary (efficacy) outcome.

15.2.1 Precision Analysis

A simulation study was conducted where a dataset with a sample size of 160 was generated where each participant had a binary feasibility outcome generated from a Bernoulli distribution with $p = 0.75$ because the goal rate for the outcome is 75%. The 95% confidence interval halfwidth was then calculated using the Wilson method. This process was repeated 100,000 times. The average 95% confidence interval halfwidth was calculated across the 100,000 simulated datasets.

[figure not shown]
Also considered in the simulation study were different sample sizes and proportion used for generating the binary outcome. Different sample sizes (40, 80, 120, 160, 200, 400) were included to gauge the effect of decreased and increased sample sizes on 95% confidence interval halfwidths as an increase in sample size does not have a constant effect on halfwidth. Different proportions (0.5, 0.6, 0.75) were considered for generating the binary outcome because, generally, as a proportion approaches 0.5 or 50% the variability increases. An increase in variability directly increases confidence interval halfwidth.

Results are presented in the table and graph below. At a sample size of 160 and a proportion of 0.75 (75%), the average 95% confidence interval halfwidth is approximately 0.066. That is, the 95% confidence interval would have about 6.6% on each site. For example, a confidence interval in this setting would look something like $\hat{p} - 0.066$ to $\hat{p} + 0.066$ where \hat{p} is whatever the estimate percentage is. The halfwidth increased up to only 7.6% for the sample size of 160 when a proportion of 0.5 was used. Only relatively marginal decreases in halfwidth occurred up to a sample size of 400. A total sample size of 160 is considered appropriate for this study.

Table 7: Confidence Interval Halfwidth for Primary (Feasibility) Outcome

Feasibility Metric Assumption (%)	Total Sample Size	Average 95% Confidence Interval Halfwidth
50%	40	0.146
	80	0.106
	120	0.088
	160	0.076
	200	0.068
	400	0.049
60%	40	0.144
	80	0.104
	120	0.086
	160	0.075
	200	0.067
	400	0.048
75%	40	0.128
	80	0.093
	120	0.076
	160	0.066
	200	0.059
	400	0.042

Figure 2: Plot of Confidence Interval Halfwidth by Sample Size for Primary (Feasibility) Outcome

15.2.2 Power Analysis

Similarly, power analysis via simulation studies was conducted for the secondary (efficacy) outcome. Since participants enrolled with cocaine use disorder and participants enrolled with methamphetamine use disorder are analyzed separately, a sample size of 80 is used. Participants randomly assigned to receive the sham rTMS had their number of negative UDS generated from a binomial distribution with $n = 8$ and $p = 0.36$. The probability of 0.36 for a negative UDS was based on the results found in Terraneo et al. (2016) when comparing rTMS to control on cocaine use. They found, at baseline, an average of about 4.5 use days per week. This would mean then that there's roughly $4.5/7 = 0.64$ probability of use on any given day and thus about 0.36 probability of no use on any given day. Although the UDS look-back period may be roughly 3 days, so that to be truly negative a participant would have to be not using for past 3 days, which may mean that true probability of negative UDS may be less than 0.36, a proportion further from 0.5 (holding all else constant) would generally result in higher power. Therefore, the use 0.36 is conservative in this sense. Regardless, different values were considered as well to gauge the sensitivity of the results to this assumption of 0.36. This same base probability, p , in the sham group is used for methamphetamine as well because no results on methamphetamine use when studying rTMS have been found. Participants randomly assigned to real rTMS had their number of negative UDS generated from a binomial distribution with $n = 8$ as well, but with p varying based on the effect sized used. In the same paper by Terraneo et al. (2016), they found roughly a 6.5 odds ratio (OR) for any use. The power analyses performed here considers a few lower, more conservative, odds ratio levels of 2, 3, 4, and 5. This includes the clinically meaningful odds ratio of 2. In order to match the model to be fit and to allow correlation between UDS from the same participant, a

random effect from a normal distribution was added to the logit of the probability value used to generate the number of negative UDS for each participant, with fixed standard deviation. The standard deviation used was determined based on a small set of possible within-participant correlation, or intraclass correlation (ICC), values. Specifically, ICCs of 0.25 and 0.5 were considered, relating to standard deviations of about 1.05 and 1.81 respectively based on the latent variable method of Goldstein, Browne, and Rasbash 2002.

Once the dataset was simulated, a mixed effect logistic regression model was fit with only binary treatment (1 for real rTMS), binary stratum, week, and site as fixed effects and a random effect to account for correlation between UDS from the same participant. Each weekly UDS enters the model as a binary response. If the model estimation procedure had issues with not being positive definite, the model was refit with the random effect removed. Once the model was fit, it was determined whether the treatment covariate was significant or not at the 0.05 confidence level (i.e., if the p-value was less than 0.05). If the covariate was significant, the treatment effect was considered significant. This process, along with data generation, was repeated 10,000 times. The proportion of times the treatment effect was considered to be significant was the power. A power of at least 80% was desired.

[figure not shown]
The power to detect a significant treatment effect decreases as treatment effect size and sample size decrease. To this end, the simulation study also considered other sample sizes (40, 60, and 100) and different treatment effect sizes, with the highest odds ratio being 5 and the lowest being 2, a clinically meaningful level. Note that this range of odds ratios is below the estimate found in Terraneo et al. (2016), (of 6.5) for a similar outcome. As previously mentioned, differing proportions in the sham rTMS arm are also considered to gauge the sensitivity of the results to the assumption of 0.36, specifically 0.26 and 0.46 were also considered.

The results are presented in the table and plot below. In both, the treatment effect is classified based on Cohen's h (Cohen 1988) as medium. With the assumption of a 0.36 baseline probability in the sham rTMS group, regardless of the ICC used, a sample size of 80 shows power of 80% or greater for an odds ratio of at least 4. That is, it achieves greater than 80% power at an odds ratio of 4, well below the effect size Terreneo et al found for a similar outcome. A clinically meaningful odds ratio of 2 does not reach 80% power at any considered sample size, including 100, under any scenario. The results do not appear to be overly sensitive to the assumption of a 0.36 baseline probability in the sham rTMS group, as the results for 0.26 and 0.46 are very similar. The results however were dependent on assumed ICC. Because of this, a sample size of 60 requires an odds ratio of at least 5 when the ICC is 0.5. While this study isn't directly powered for efficacy, the results presented here show that a sample size of 80 allows greater than 80% power to detect a significant treatment difference at reasonable, medium-sized, treatment effects (lower than found in a similar study with a similar outcome), is relatively robust to assumptions made in the power analysis, and the use of a sample size of 80 for both MUD and CUD is, therefore, reasonable.

Table 8: Power Analysis Results for Secondary (Efficacy) Outcome

ICC	Baseline Probability	Odds Ratio	Treatment Effect Size	Power			
				N = 40	N = 60	N = 80	N = 100
0.25	0.26	2.0	Medium treatment effect	41%	53%	66%	75%
		3.0		77%	90%	96%	99%
		4.0		92%	99%	100%	100%
		5.0		97%	100%	100%	100%
	0.36	2.0		43%	56%	67%	75%
		3.0		78%	90%	96%	99%
		4.0		92%	98%	100%	100%
		5.0		97%	100%	100%	100%
	0.46	2.0		43%	55%	67%	76%
		3.0		77%	90%	96%	99%
		4.0		91%	98%	100%	100%
		5.0		97%	100%	100%	100%
0.5	0.26	2.0	Medium treatment effect	22%	27%	33%	40%
		3.0		43%	57%	67%	77%
		4.0		60%	75%	86%	92%
		5.0		72%	86%	94%	97%
	0.36	2.0		23%	29%	35%	42%
		3.0		43%	58%	69%	77%
		4.0		60%	75%	86%	92%
		5.0		72%	86%	94%	97%
	0.46	2.0		22%	28%	33%	41%
		3.0		43%	55%	67%	76%
		4.0		59%	75%	86%	92%
		5.0		71%	85%	94%	97%

Figure 3: Plot of Power by Sample Size and Treatment Effect for Secondary (Efficacy) Outcome

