2.3 Sample Size and Study Population

Approximately 160 adults (aged 18-65) with moderate to severe cocaine use disorder (CUD; n=80) or methamphetamine use disorder (MUD; n=80) interested in cutting down or stopping use will be recruited. Participants who meet DSM-5 criteria for both CUD and MUD will be asked to choose which is the primary substance of choice to determine their diagnostic category. The study will be conducted across 4 sites (with 2 sites – Wake Forest, UT Health San Antonio – discontinuing study participation early), and it is estimated that up to 80 participants will be enrolled at each site. Sites may vary on total enrolled per site, but no more than 160 total participants will be enrolled across all sites. This sample size provides adequate confidence interval length and provides greater than 80% power to detect medium-sized effect sizes, measured as odds ratios, of greater than 4 with a two-sided hypothesis test and significance level of 0.05 within each of CUD and MUD separately. Randomization will be stratified based on current major depressive episode (MDE), study site and CUD or MUD.

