15.4 Significance Testing

The secondary (efficacy) outcome will be evaluated using a two-sided test on the significance of the treatment parameter in the proposed model with a type I error rate of 5%. No attempt will be made to control family-wise type I error rate when testing for CUD and MUD participants. No other hypothesis testing will be performed on the primary or secondary outcomes.

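### The plan labels odds ratios 2 to 5 as medium and claims over 80% power for medium effects with 80 per use-disorder group, but in its own table only odds ratios of 4 or more exceed 80% at both ICCs

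*Protocol*

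**What the plan says.** The efficacy comparison is made separately in cocaine and methamphetamine use disorder, so in the power simulation "a sample size of 80 is used" for each. Protocol 15.2.2 tabulates power in Table 8 for odds ratios 2, 3, 4 and 5, sham probabilities 0.26, 0.36 and 0.46, and ICCs 0.25 and 0.5. It says of the table and the plot that "the treatment effect is classified based on Cohen's h (Cohen 1988) as medium". In Table 8, medium is the only effect-size label printed.

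The section concludes that "a sample size of 80 allows greater than 80% power to detect a significant treatment difference at reasonable, medium-sized, treatment effects", and calls the result relatively robust to the assumptions. SAP 10.2 carries the same text. Protocol 2.3 says that the sample size "provides greater than 80% power to detect medium-sized effect sizes, measured as odds ratios, of greater than 4" within each disorder, and 15.1.3 says much the same.

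Protocol 15.2.2 also states that 80% power at N = 80 needs an odds ratio of at least 4, that OR 2 (called clinically meaningful) does not reach 80% in any scenario, that the results depend on the ICC, and that the study is not directly powered for efficacy.

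**The concern.** If the effects in the table are medium, then over 80% power at medium-sized effects should hold for the rows in the table. It fails for OR 2 at both ICCs and for OR 3 at the higher ICC. The robustness remark also sits badly beside the statement, in the same paragraph, that power depends on the ICC.

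This sentence is part of the case for 80 per group, and it is the summary a reader is likely to carry into the results. Someone told that the trial had over 80% power for medium effects could read a null efficacy result as stronger evidence than it is, particularly against OR 2 or 3. Efficacy is a secondary outcome, so the primary feasibility result is not touched.

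**Working it through.** **Inputs (Protocol 15.1.4, 15.2.2 and 15.4).** N = 80 per disorder with 1:1 allocation, so 40 per arm; 8 weekly urine screens per participant; sham probability 0.36; odds ratios 2 to 5; random-intercept SD 1.05 (ICC 0.25) or 1.81 (ICC 0.5); two-sided 5% test; target power 80%.

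**Step 1: reproduce Table 8.** Data were simulated from logit(p) = logit(0.36) + log(OR) × treatment + u, with u normal with mean 0 and the stated SD. A random-intercept logistic model with treatment, stratum and site was fitted by Gauss-Hermite quadrature with a Wald test (4,000 to 6,000 runs per scenario). Week was left out of the fit because the generated data have no week effect.

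| ICC | OR | Table 8, N = 80 | Simulated |
|---|---|---|---|
| 0.5 | 2 | 35% | 33.5% |
| 0.5 | 3 | 69% | 66 to 67% |
| 0.5 | 4 | 86% | 84.3% |
| 0.5 | 5 | 94% | 93.3% |
| 0.25 | 2 | 67% | 66.4% |
| 0.25 | 3 | 96% | 95.8% |

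Agreement is within 2 points except for OR 3 at ICC 0.5, which is 2 to 3 points low; a Laplace fit gives 68.5% there. The printed entries can be relied on.

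**Step 2: set the claim against the table.** At baseline 0.36 the rows below 80% are OR 2 at ICC 0.5 (80 − 35 = 45 points short), OR 3 at ICC 0.5 (80 − 69 = 11 points short) and OR 2 at ICC 0.25 (80 − 67 = 13 points short). At baselines 0.26 and 0.46 the same rows read 33%, 67% and 66 to 67%. This step uses no outside benchmark.

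**Step 3: robust to what?** At N = 80, moving the baseline between 0.26 and 0.46 changes any entry by at most 2 points. Moving the ICC from 0.25 to 0.5 changes OR 2 by 67 − 35 = 32 points and OR 3 by 96 − 69 = 27 points. The result is robust to the baseline probability but not to the ICC.

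**Step 4: does one label fit?** Cohen's h = 2·asin(√p₁) − 2·asin(√p₀). The sham odds are 0.36/0.64 = 0.5625, and 2·asin(√0.36) = 1.287.

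- On the stated (conditional) probabilities, OR 2, 3, 4 and 5 give p₁ = 0.529, 0.628, 0.692 and 0.738, so h = 0.34, 0.54, 0.68 and 0.78.
- On population-averaged probabilities, obtained by averaging each arm's probability over the random intercept, h = 0.22, 0.35, 0.44 and 0.51 at ICC 0.5, and 0.28, 0.44, 0.56 and 0.64 at ICC 0.25.

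The documents print neither cut-offs nor the scale used. With the usual benchmarks (0.2 small, 0.5 medium, 0.8 large; an assumption here), OR 2 falls short of 0.5 on every scale. If medium means the band from 0.5 to 0.8 on the conditional scale, OR 3 is in it and still has 69% power at ICC 0.5.

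**Step 5: power at exactly h = 0.5.**

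- Conditional scale: p₁ = 0.607, OR 2.75. Simulated power is 59.7% at ICC 0.5 (Monte Carlo SE about 0.6 points) and about 92% at ICC 0.25. Interpolating Table 8 at ICC 0.5 gives 60.5% (linear) or 62.0% (probit on log OR).
- Population-averaged scale: OR 3.45 at ICC 0.25 and OR 4.81 at ICC 0.5. At N = 80, Table 8 brackets these with 96% to 100% and 86% to 94%.

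**The case against.** The strongest reply is that nothing is hidden and no figure is wrong. Protocol 2.3 and 15.1.3 attach the OR 4 threshold in the same sentence as the word medium. Protocol 15.2.2 prints every power value, concedes OR 2, notes the ICC dependence and disclaims direct powering for efficacy. On that view the quoted sentence merely summarises these statements. If medium is the band from 0.5 to 0.8 on the conditional scale, OR 4 and OR 5 do belong to it. All of this stands, and it keeps the point modest. It does not rescue the summary sentence, because the classification is applied to the table and plot as a whole, with no odds ratio excepted. The blanket reading rests on that sentence more than on the layout of the table cell.

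A second reply is that later work overtakes the claim. SAP 11.1.1, using updated screen variability and sham probability, reports 94% power for OR 3 at n = 52 and 73.2% for OR 2 at n = 80, so ICC 0.5 may be pessimistic. SAP 7.10 records that the planned models could not be completed after database lock, so relabelling alters no analysis. Both are fair. SAP 10.2 nevertheless repeats the sentence unchanged, and the re-estimate still leaves OR 2 below 80% at 80 per group; it puts the requirement at 92.

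A reader might go further and infer that the trial has only about 60% power for a medium effect. The documents do not support that as a general statement. It needs an unprinted benchmark (h = 0.5), the conditional scale and ICC 0.5 all together. At ICC 0.25 the figure is about 92%, and on population-averaged probabilities power at h = 0.5 exceeds 80% at both ICCs. Protocol 15.2.2 derives 0.36 from an average number of use days per week, so the population-averaged scale cannot be dismissed.

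**Conclusion.** The point holds as an error of labelling and conclusion. Over 80% power at medium-sized effects is not true of the effects the plan itself calls medium: at N = 80 and baseline 0.36, OR 2 has 35% (ICC 0.5) or 67% (ICC 0.25), and OR 3 has 69% at ICC 0.5. Of the tabulated values, only OR 4 and OR 5 exceed 80% at both ICCs. This rests on the plan's printed figures and on reading its classification as covering the whole table. That no single label fits OR 2 to 5 rests additionally on the usual h benchmarks, and it holds on both probability scales.

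Two further inferences are not supported. Table 8 is not miscalculated, since it reproduces closely. Nor can one say that a null result would exclude only odds ratios of about 4 or more: at ICC 0.25 power for OR 3 is 96%, and the planned report includes an odds ratio with a 95% confidence interval, which is the proper basis for reading a null. The practical weight is modest.

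**What to change.** In Protocol 2.3, 15.1.3 and 15.2.2 and in SAP 10.2 (or in the SAP and final study report, if the protocol will not be amended again):

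- Delete medium-sized. State that 80 per use-disorder group gives at least 80% power for an odds ratio of 4 or more at ICC up to 0.5; that OR 3 reaches 80% at ICC 0.25 (96%) but not at ICC 0.5 (69%); and that OR 2 reaches it at neither.
- Limit the robustness statement to the baseline probability, and say that power depends on the ICC.
- In Protocol Table 8, SAP Table 3 and the matching plots, replace the single label with h for each odds ratio and name the scale. At baseline 0.36 these are 0.34, 0.54, 0.68 and 0.78 (conditional), or 0.22, 0.35, 0.44 and 0.51 (population-averaged, ICC 0.5).
- If power at h = 0.5 is quoted at all, give it with its conditions: about 60% at OR 2.75 and ICC 0.5, using the usual benchmark and the conditional scale.

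The cost is a few sentences and one table column, with no new participants or analyses. The one downside is that the stated sensitivity of the trial reads slightly less favourably.

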15.2.3 Projected Number of Sites

Four study sites will participate in the study.

15.2.4 Projected Number of Participants per Site

Each study site will enroll approximately 40 (20 for each of CUD and MUD) participants, with the goal of randomizing approximately 160 (80 for each of CUD and MUD) participants across the 4 study sites.

15.3 Statistical Methods for Primary and Secondary Outcomes

15.3.1 Primary (Feasibility) Outcome

The primary feasibility outcome of the percentage of participants who receive 20 or more rTMS sessions will be summarized by the estimated percentage and a 95% confidence interval by the Wilson method. This method was chosen over others, including an exact or Clopper-Pearson method because the Wilson method has shown to have better performance than exact or Wald methods (Brown et al., 2001.). There is no hypothesis testing. The corresponding shell SAS code is provided below.

```
proc freq data = dat;
  table y / binomial(cl = wilson);
run;
```

y is the binary variable indicating whether the participant received at least 20 rTMS treatment sessions.

15.3.2 Secondary (Efficacy) Outcome

The secondary (efficacy) outcome will be analyzed with a generalized linear mixed model approach to adjust for correlation between UDS from the same participants and to provide conditional interpretation of the treatment effect. The model will include fixed effects for treatment, MDE, week, and site and a random effect for participant. It is important to note that a binary response of negative UDS, for each UDS provided by each participant, will be used as the outcome as opposed to just their percentage of negative UDS. The model used still allows inference on the overall probability of a negative weekly UDS during the treatment period. Additionally, week will enter the model as a categorical variable to allow greater flexibility on the effect of week.

The assessment of the significance of the treatment will be done by testing the significance of the treatment parameter at the 0.05 significance level. The treatment effect will be measured by an odds ratio with an associated 95% confidence interval. The corresponding shell SAS code is provided below.

```
proc glimmix data = dat method = quad;
  class site week participant;
  model y(event = '1') = trt mde week site / dist = binary link
  = logit;
  random intercept / subject = participant;
run;
```

dat is a dataset with one row per weekly UDS per participant. y is the a binary variable with a value of 1 indicating the UDS for that participant was negative, trt is a binary variable with a value of 1 indicating real rTMS and 0 indicating sham rTMS, mde is a binary variable with a value of 1 indicating the presence of MDE, week is the study week, and site is a categorical variable containing which of the sites each participant was enrolled in.

In the event that the estimate of the variance component related to the within participant correlation is so close to 0 that it causes the overall covariance matrix to not be positive definite, the model will be refit without the random effect for the correlation within participant. This is accomplished simply by removing the line starting with random in the shell SAS code shown above.

An odds ratio (as the exponential of the trt coefficient), along with 95% confidence interval, will be provided to assess the effect of treatment. An odds ratio of greater than 1 would indicate an increased odds of a negative weekly UDS for active rTMS versus sham rTMS during the treatment period. That is, a positive effect of rTMS versus sham. Similarly, a value of less than 1 indicates a decreased odds of a negative weekly UDS for active rTMS versus sham rTMS during the treatment period. That is, a negative effect of rTMS versus sham. A p-value will also be provided to test the significance of the effect.

The model and results will be conducted and presented separately for those participants randomized with CUD or MUD.

